### 1.0 Objectives

1.1 Purpose: The objective of this study is to assess the effect of standardized scalp care, specifically mechanical cleansing with the Venus Glow™ Device and water, on the scalp microbiome. This study also seeks to characterize the microbiome of the normal, healthy scalp, thereby providing a baseline for which the scalp affected by hair and scalp disease can be compared.

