### 3.0 Study Endpoints/Events/Outcomes

- 3.1 Primary Endpoint/Event/Outcome: The primary endpoint will be scalp swab assessment of scalp microbiome composition before and after Venus Glow™ treatment. Our hypothesis is that there will be a decrease in microbe burden on the scalp with treatment.
- 3.2 Secondary Endpoint(s)/Event(s)/Outcome(s): Secondary endpoint includes scalp swab assessment of scalp microbiome composition after participants have returned to their normal hair and scalp care routine, providing information about the normal, healthy scalp microbiome. In addition, photography comparisons with the HairMetrix device will be taken before each treatment at the swab sites for each participant.

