### 5.2 Study Procedures:

## MEDICAL PROTOCOL (HRP-590)

PROTOCOL TITLE: Effect of mechanical intervention on the scalp microbiome: setting the stage for the future management of cicatricial alopecias

[figure not shown]
VERSION DATE: 05 August 2023

Subjects will come for Venus Glow™ treatments, two treatments over a two week period. At the first visit they will complete an initial questionnaire regarding current scalp care practices, skin type, and hair type. An initial baseline scalp swab and HairMetrix photography in the two swab sites will be taken at the beginning of this visit. Treatment with the Venus Glow™ device will also occur. To treat, the scalp will be divided into four quadrants. In the right two quadrants, the hair will be sectioned into both vertical and horizontal parts about 1 cm apart. The tip of the device will then be dragged in zig zag movements along vertical part widths, then along horizontal part widths, and then once more along the vertical part widths, to account for a total of three passes. The left side will not be treated with the device.

Swab samples will be collected from the untreated right mid-frontal scalp, treated right mid-frontal scalp, and the untreated left mid-frontal scalp and will be collected at the first baseline and concurrent treatment session, second treatment session and 3-6 days after the last treatment when participants have returned to their usual cleansing routine. In addition, HairMetrix photography will be taken in the two swab sites (right scalp swab site and left scalp swab site) before treatment at the first baseline and concurrent treatment session, the second treatment session and the follow-up session 3-6 days after the last treatment.

All swabs will be taken 10 cm from the nasal bridge and 3 cm from the midline (see Photo 1 below). Subjects will avoid shampooing, chemical, or heat treatments, but will be able to wet their hair during the study.

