## MEDICAL PROTOCOL (HRP-590)

PROTOCOL TITLE: Effect of mechanical intervention on the scalp microbiome: setting the stage for the future management of cicatricial alopecias

VERSION DATE: 05 August 2023

|  |   |
|--|---|
|  | 

• Swab of right and left mid-frontal scalp prior to treatment

• HairMetrix photography before treatment

• Right side of scalp treatment with the Venus Glow™ device and brush (left side will not be treated)

• Swab of right mid-frontal scalp post- treatment

   |
| Beginning of Week 1 - Second Treatment
(+/- 3 days) | 

• Participant report of adverse events

• Swab of right and left mid-frontal scalp prior to treatment

• HairMetrix photography before treatment

• Right side of scalp treatment with the Venus Glow™ device and brush (left side will not be treated)

• Swab of right mid-frontal scalp post-treatment

 |
| End of Week 1- Final Visit (+/3 days)                   | 

• Participant report of adverse events

• Swab of right and left mid-frontal scalp

• HairMetrix photography

  |

All participants will have a final 3-6 day visit and swab collection after their treatments have been completed and they have returned to their typical hair and scalp care routine, described above. All visits including this final visit will be compensated at \$10 per visit. If a patient happens to miss a study visit, one of the study staff will reach out to the patient via a phone call.

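### Section 3.2 ties the healthy-scalp reference only to the post-treatment final swab, although device-free Week 0 swabs from both sides are already collected

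*Combined protocol and SAP*

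**What the plan says.** **Objective (section 1.1).** Besides the device question, the study aims to "characterize the microbiome of the normal, healthy scalp, thereby providing a baseline" against which diseased scalp can later be compared. No time point is named.

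**Endpoint (section 3.2).** The secondary endpoint includes "scalp swab assessment of scalp microbiome composition after participants have returned to their normal hair and scalp care routine", and the clause that follows gives its purpose: "providing information about the normal, healthy scalp microbiome". No other endpoint mentions this purpose. The primary endpoint in section 3.1 covers composition before and after treatment, but as a device question.

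**Timing (section 5.2).** Participants have "two treatments over a two week period", on the right side only. The last swab comes "3-6 days after the last treatment when participants have returned to their usual cleansing routine". The same section also says: "Subjects will avoid shampooing, chemical, or heat treatments, but will be able to wet their hair during the study".

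**Schedule (section 5.3).** The Week 0 visit lists "Swab of right and left mid-frontal scalp prior to treatment". The second visit repeats that line, and the final visit swabs both sides once more. The Week 0 questionnaire records time since last shampoo and products used since then. No repeat is listed at the final visit.

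**Analysis (section 15.1).** The plan covers the treated-versus-untreated comparison of change, the HairMetrix images, and demographic and clinical factors that may modify the device effect. It has no analysis of the healthy-scalp characterisation.

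**The concern.** A healthy reference should come from skin that the study has not altered. The one sample that the plan links to this aim is taken after the intervention.

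The protocol's own premises make this matter. Section 3.1 hypothesises that treatment lowers the microbial burden. If that happens and persists for some days, the right-side final swab carries part of the effect. Section 2.1 says that hygiene practices may play a role and that their effect on the scalp microbiome is little known. The plan therefore cannot take a period without shampoo to be harmless, and that period applies to both sides.

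Since the reference is meant for later comparison with scalp disease, a shift in it would pass into those comparisons.

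**Working it through.** The plan gives no figure on this point. The power statement in section 15.2 concerns the treated-versus-untreated comparison and does not bear on it. The check is therefore a reconciliation of the schedule, plus swab counts.

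**Step 1: exposure at each swab that could serve as the reference** (sections 5.2 and 5.3)

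| Swab | Device treatments, right | Device treatments, left | Study shampoo avoidance | Shampoo history recorded |
|---|---|---|---|---|
| Week 0, before treatment | 0 | 0 | not yet begun | yes |
| Second visit, before treatment | 1 | 0 | in force | none listed |
| Final visit | 2 | 0 | at least part of it has passed | none listed |

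Only the Week 0 swabs are free of both exposures on both sides.

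**Step 2: the two readings of the shampoo instruction.** If avoidance lasts for the whole study, the final swab is taken under avoidance, and the return to routine in sections 3.2 and 5.2 has not happened. If avoidance ends after the second treatment, at most 3-6 days of usual care precede the final swab. The documents give no evidence that the flora has recovered by then. On both readings the interval between the two treatments falls under avoidance, so both sites have been through at least part of it.

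**Step 3: counts.** Swabs per time point = 2 sides x N.

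- N = 20 (section 5.1): 2 x 20 = 40 swabs at Week 0. The final visit also gives 40, of which 20 are from the treated side.
- N = 25 (section 5.1): 2 x 25 = 50 swabs at Week 0. The final visit also gives 50, of which 25 are from the treated side.
- N = 40 (sections 10.1 and 25.1, which do not match section 5.1): 2 x 40 = 80 at each of the two visits, of which 40 at the final visit are from the treated side.

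These are paired sites. With within-person correlation r, the information in a mean equals that of 2N/(1 + r) independent swabs. The documents give no r. Over the assumed range from r = 1 to r = 0, this runs from 20 to 40 at N = 20 and from 25 to 50 at N = 25. Choosing Week 0 costs nothing in sample count, because the totals are the same.

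**Step 4: where distortion could enter.** For one taxon, on a suitable scale, let m be the healthy mean, d the device effect remaining on the right side at the final visit, and s the remaining effect of shampoo avoidance on both sides. Assume the device does not affect the left side. Then:

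- Week 0, both sides: m
- Final visit, left side only: m + s
- Final visit, right side only: m + s + d
- Final visit, both sides averaged: m + s + d/2

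The documents give neither s nor d. Either may be near zero. Only the Week 0 choice does not depend on them.

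**The case against.** The strongest reply is that section 3.2 is looser than a rule. It says the endpoint *includes* this swab and that the swab is informative about healthy scalp. It neither names the swab as the sole reference nor excludes Week 0. Section 3.1 already has composition assessed before treatment, so the baseline swabs will be sequenced and can be described. The aim is descriptive, with no test, alpha or power attached. All of this stands, so no data are lost. But the only stated link between the aim and a sample points to the final visit, and section 15.1 does not correct it. The choice is then left until results are known.

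The left side is never treated, so a left-only final reference would have no direct device exposure. That also stands, but section 3.2 does not restrict the reference to the left side, and the left side still follows shampoo avoidance.

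The days of usual care before the final swab are the protocol's own safeguard and may be enough. The documents neither show nor refute this.

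Week 0 is not a standardised state either. Participants arrive with differing times since shampoo and differing products. This is a real but small drawback, and the Week 0 questionnaire allows that variation to be described. No such record is listed for the final visit.

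A reader might go further and infer that half of the reference samples are contaminated, or that the reference is biased by the full device effect. The documents do not support either. No pooling of sides is stated, and only an effect that persists to the final visit could enter.

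**Conclusion.** The point holds as a mis-assigned sample for a secondary, descriptive aim. As written, the healthy-scalp reference is linked only to a post-intervention swab: two treatments on the right, none on the left, and at least part of the shampoo avoidance on both. A cleaner set of equal size, 40-50 correlated swabs at 20-25 participants, is already scheduled at Week 0.

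The direction and size of any distortion are unknown. The conclusion does not rest on carry-over being large. It rests on the schedule, and on the absence of evidence in the documents that either exposure has washed out by the final visit. It would be wrong to infer that the plan forbids the baseline swabs or that the reference is shown to be biased. The primary comparison is unaffected. The change is worth making because it is nearly free and the reference is meant for reuse.

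**What to change.** 1. **Section 3.2.** State that the healthy-scalp characterisation uses the Week 0 pre-treatment swabs from both sides. Describe the final-visit swab as a recovery or persistence endpoint, reported separately for the treated and untreated sides.
2. **Section 15.1.** Add the matching analysis: Week 0 composition with participant as a cluster or random effect, and days since last shampoo and products used described from the existing questionnaire. Add a by-side description of the final visit.
3. **Section 5.2.** Reconcile the instruction to avoid shampoo throughout the study with the statement that usual cleansing has resumed before the last swab. Which is intended is for the investigators to settle.
4. **Sections 5.1, 10.1 and 25.1.** Align the participant numbers, so that the swab count behind the reference is clear.

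The cost is a few sentences in a protocol amendment, with no new samples, visits or data and no change to the primary analysis. Repeating the shampoo-timing question at the final visit would be optional, and would help in reading the recovery endpoint.

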### 4.0 Study Intervention(s)/Investigational Agent(s)

#### 4.1 Description:

Venus Glow™ device is an FDA Class 1 device used for cosmetic treatments. The device utilizes hydradermabrasion to clean and remove debris from the skin. Hydradermabrasion is a form of microdermabrasion that utilizes a crystal-free exfoliation tip with water and often a method for suction. To complete such treatment, the Venus Glow™ device employs a hand-piece functional with a rotating tip, two 70-micron jets, and a vacuum. The rotating tip and jets allow for dispersion of a selected solution to clean and the vacuum allows for removal of debris via the suction.

Our off-label design utilizes the Venus Glow™ device, but with device setting adjustments optimized for scalp health. The device will be set to the weakest injection setting (setting 1) given we are not injecting serums and intend to wet only the scalp, not the hair fibers. The suction will be set to the maximum setting (setting 3) to allow for ample removal of debris. No sensitivity or adverse events such as bruising have been seen when using this setting on the scalp. Finally, the rotation will be set to the medium setting (setting 2) to allow for a moderate cleansing without unnecessary exfoliation.

## MEDICAL PROTOCOL (HRP-590)

PROTOCOL TITLE: Effect of mechanical intervention on the scalp microbiome: setting the stage for the future management of cicatricial alopecias

VERSION DATE: 05 August 2023

We believe this device may be a non-significant risk device as it:

- is not an implant and does not present a potential for serious risk to the health, safety, or welfare of a participant;
- is not purported and will not be represented to be for use supporting or sustaining human life and presents a potential for serious risk to the health, safety, or welfare of a participant;
- will not be used of substantial importance in diagnosing, curing, mitigating, or treating disease, or otherwise preventing impairment of human health and does not present a potential for serious risk to the health, safety, or welfare of a participant; or
- does not otherwise pose a potential for serious risk to the health, safety, or welfare of a participant.

### 4.2 Drug/Device Handling:

The off-label Venus Glow™ device will be stored in the University of Minnesota Department of Dermatology in the Phillips-Wangensteen building, Maple Grove clinic or the Clinics and Surgery Center. Additional supplies will be stored separately in the respective clinics.

While wearing gloves, the device and treatment room will be wiped down with disinfectant wipes after each use. The handpiece tips will be changed in between each subject visit. Gloves and masks will be utilized by the study staff that is administering the treatment. Participants will be asked to follow the current CDC guidelines regarding COVID-19.

4.3 Biosafety: N/A - The research does not involve a recombinant or synthetic nucleic acid, human gene transfer, biologically derived toxin, or an infectious agent.

4.4 Stem Cells: N/A - The research does not involve stem cells.

4.5 Fetal Tissue: N/A - The research does not involve fetal tissue.

## 5.0 Procedures Involved

5.1 Study Design: This is a research study utilizing scalp swabs to evaluate the efficacy of the Venus Glow™ device treatment on the scalp microbiome. Healthy participants who have not been diagnosed with scalp or hair disease will be followed over a period of 2 weeks to assess their scalp microbiome and see how well the investigational device works on decreasing the microbe burden of the scalp.

*Total Enrollment (N= 20-25):* A total of up to 25 subjects between the ages of 18-50 years with different self-reported ethnicities and evaluated skin and hair types will be enrolled in the study.

### 5.2 Study Procedures:

## MEDICAL PROTOCOL (HRP-590)

PROTOCOL TITLE: Effect of mechanical intervention on the scalp microbiome: setting the stage for the future management of cicatricial alopecias

[figure not shown]
VERSION DATE: 05 August 2023

Subjects will come for Venus Glow™ treatments, two treatments over a two week period. At the first visit they will complete an initial questionnaire regarding current scalp care practices, skin type, and hair type. An initial baseline scalp swab and HairMetrix photography in the two swab sites will be taken at the beginning of this visit. Treatment with the Venus Glow™ device will also occur. To treat, the scalp will be divided into four quadrants. In the right two quadrants, the hair will be sectioned into both vertical and horizontal parts about 1 cm apart. The tip of the device will then be dragged in zig zag movements along vertical part widths, then along horizontal part widths, and then once more along the vertical part widths, to account for a total of three passes. The left side will not be treated with the device.

Swab samples will be collected from the untreated right mid-frontal scalp, treated right mid-frontal scalp, and the untreated left mid-frontal scalp and will be collected at the first baseline and concurrent treatment session, second treatment session and 3-6 days after the last treatment when participants have returned to their usual cleansing routine. In addition, HairMetrix photography will be taken in the two swab sites (right scalp swab site and left scalp swab site) before treatment at the first baseline and concurrent treatment session, the second treatment session and the follow-up session 3-6 days after the last treatment.

All swabs will be taken 10 cm from the nasal bridge and 3 cm from the midline (see Photo 1 below). Subjects will avoid shampooing, chemical, or heat treatments, but will be able to wet their hair during the study.

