## **15.0 Statistical Considerations**

*15.1 Data Analysis Plan:*

The primary analysis will evaluate whether there is a difference in the baseline and 2-week change in the relative abundance of pre-specified bacteria (approx. 20) between the device-treated portion of the scalp and the non-treated portion. In order to account for the within-subject correlation, mixed-effects models will be performed. As a secondary analysis, we will compare the HairMetrix images and analyze how various demographic and clinical factors such as sex and skin type impact the effect of the device.

*15.2 Power Analysis:*

Limited data are available to inform a power/sample size estimate. However, if there is a total of 38 subjects (40 initial, with 5% dropout), then we will have pre- and post-treatment data for 38 device-treated, and 38 non-treated portions of the scalp. Even when ignoring the within-subject correlation, this will allow us to have 80% power to detect an effect size of 0.7 (difference in the baseline to week 1 change between groups), assuming an alpha of 0.05.

*15.3 Data Integrity:*

- The study monitor will ensure that the investigation is conducted according to protocol design and regulatory requirements. The monitor will provide ongoing monitoring of data validity and regulatory issues (e.g., eligibility determinations, consent form process, serious adverse event reporting, IRB actions, disclosures of conflict of interest).
- Study records will be monitored at regular intervals by the study monitor. The monitor will perform source data verification and as such must be given access to the subject's primary source documentation, such as paper or electronic medical records such as consent to participate in the study, visit dates, demographic information, adverse events, concomitant medications, drug accountability, etc. that support data entries in the CRF.

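### The device always goes on the right and the control is always the left, so a right-left difference in change over time cannot be separated from the device effect in the primary contrast

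*Combined protocol and SAP*

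**What the plan says.** Section 5.2 divides the scalp into four quadrants and confines the device to one half: "In the right two quadrants, the hair will be sectioned into both vertical and horizontal parts about 1 cm apart". It then states "The left side will not be treated with the device". The visit table in section 5.3 repeats this at both treatment visits: "Right side of scalp treatment with the Venus Glow™ device and brush (left side will not be treated". No section randomises, alternates or counterbalances the side, and there is no untreated group of participants.

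Swabbing differs by side. At each treatment visit both sides are sampled first ("Swab of right and left mid-frontal scalp prior to treatment"), but after treatment only the right is sampled again ("Swab of right mid-frontal scalp post- treatment"). At the final visit both sides are sampled once.

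Section 15.1 defines the primary comparison as the difference in change from baseline "between the device-treated portion of the scalp and the non-treated portion". On the model it says only: "In order to account for the within-subject correlation, mixed-effects models will be performed". It mentions no side effect.

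**The concern.** In this within-person design the left side is the control. It is a valid control for change over time only if, without the device, the two sides would change alike on average. With the side fixed, that has to be assumed. Any average difference between right and left in how abundance changes is added in full to the estimated device effect, and it can create an effect or mask one.

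The study also disturbs the usual routine. Section 5.2 bars shampooing, chemical and heat treatments, and participants return to their own routine before the final swab. Both sides can be expected to change, so unequal change is possible. The questionnaire items listed in 5.3 do not include parting, sleeping side or handedness, so later adjustment for these would not be available.

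**Working it through.** **Inputs.** Side assignment: 5.2 and 5.3. Contrast: 15.1. Alpha 0.05: 15.2, which does not state sidedness; two-sided is assumed here. Enrolment 20-25: 5.1. Dropout 5%: 15.2. Analysed numbers: 20 × 0.95 = 19 and 25 × 0.95 = 23.75, taken as 24. The size of any drift is not in the documents and is assumed.

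**The plan's own figure.** Section 15.2 claims "80% power to detect an effect size of 0.7 (difference in the baseline to week 1 change between groups") with 38 treated and 38 untreated portions. A two-sided two-sample t-test with n = 38 per side and effect size 0.7 gives 85.3%, so the stated 80% is conservative. The point below does not depend on it.

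**Identifiability.** For participant i let D_i be the right-side change minus the left-side change, δ the device effect, γ the right-left drift and e_i random error.
- Device always on the right: D_i = δ + γ + e_i. Only the sum δ + γ can be estimated.
- Device side assigned: D_i = a_iδ + γ + e_i, with a_i = +1 for right and −1 for left. The group means are γ + δ and γ − δ. Half their difference is δ and half their sum is γ.

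The fixed-effects design matrix shows the same thing. With columns for intercept, side, time, side × time and treatment × time, the rank is 4 of 5 under the fixed side, because the last two columns are identical. It is 5 of 5 when both side assignments occur. This holds whichever follow-up time is used for the change.

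**Size under assumed drift.** With δ = 0, the paired t statistic has n − 1 degrees of freedom and noncentrality γ√n/σ_D, where σ_D is the SD of D_i. Two-sided rejection rates for one taxon:

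| Drift γ/σ_D | n = 24 | n = 19 |
|---|---|---|
| 0 | 5% | 5% |
| 0.1 | 7.6% | 7.0% |
| 0.2 | 15.6% | 13.1% |
| 0.3 | 29.1% | 23.6% |

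**Choice of SD.** If drift is expressed in SDs of one side's change (σ), then σ_D = σ√(2(1 − ρ)), where ρ is the between-side correlation. The documents give no ρ. At ρ = 0.5, σ_D = σ and the table is unchanged. At ρ = 0, σ_D = 1.414σ, so drifts of 0.2σ and 0.3σ become 0.141σ_D and 0.212σ_D. Rejection is then 10.2% and 16.9% at n = 24, and 9.0% and 14.1% at n = 19.

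**Effect of the remedy.** In 20,000 simulated trials at n = 24 with γ = 0.3σ and no device effect, the fixed-side design had a bias of about 0.30σ and rejected in 17% (ρ = 0) or 30% (ρ = 0.5). With balanced assignment and a side term in the change-score model, bias was about 0 and rejection about 5% in both cases. More participants do not help a fixed side: at n = 38 and ρ = 0.5 its rejection rate rises to 44%.

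**The case against.** The strongest reply is that the bias is hypothetical. Sleeping side, parting and handedness are ordinarily stable habits, and a stable difference cancels against baseline. Habits that differ between people add noise, not bias. To matter, they would have to move the right-left difference in the same direction on average within about two weeks. The documents give no reason to expect this. That stands as a limit on the size of the concern. It does not restore identifiability.

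A reader might infer that nothing in the study can tell device from side. That goes too far. The right side is swabbed before and after treatment within the same visit, section 3.1 describes the primary endpoint as before versus after treatment, and a slow side drift cannot explain a change within one session. But no repeat left swab controls that comparison for the effect of swabbing the same site twice, and it is not the contrast in 15.1.

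A reader might also infer that randomising the side would cure differences in staff technique on the known treated side. It would not: technique follows treatment, not laterality. The same goes for the brush and the extra post-treatment swab.

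Finally, enrolment status is not shown. If most participants have already been treated on the right, a change now brings less, and fixed versus assigned side would coincide with calendar time.

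**Conclusion.** The point holds as a design weakness that is cheap to remove. In the 15.1 contrast, side-by-time and device effects are fully aliased, and that is certain from the text. Whether a drift exists is unknown, so the documents do not support saying that the result is biased.

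The rejection rates run from the nominal 5% with no drift to 29% at n = 24 with a drift of 0.3 SD of the paired difference. They rest on the assumed drift, a two-sided paired t-test, normal differences and 5% dropout from 20-25 enrolled. In SDs of one side's change with uncorrelated sides, drifts of 0.2-0.3 give about 10-17% at n = 24 and 9-14% at n = 19. The case for changing the plan rests on the low cost of the remedy, not on a demonstrated bias.

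**What to change.** - In 5.2 and 5.3, replace right and left with treated and untreated side, including for the swab sites.
- Assign the treated side per participant from a pre-generated 1:1 blocked list, opened only after the baseline swabs, and record it on the form.
- In 15.1, add a side-by-time term, or a side term if change scores are modelled. In a repeated-measures model, a side main effect alone absorbs only the constant difference and leaves drift unmodelled.
- If some participants are already enrolled, apply this to the rest and report those treated on the right by default separately.
- If enrolment is complete, state that side and device are not separable in the primary contrast and interpret the result accordingly.
- State that technique, brush and extra swab still follow the treated side.

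Cost: a short amendment, an allocation list, one form field, about one degree of freedom and a small risk of labelling the wrong side. No extra visits or samples are needed.
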